3.6 ON STUDY EVALUATION

3.6.1 General Requirements

3.6.1.1 CBC with differential and platelets will be performed every two weeks during treatment. Creatinine, bilirubin, SGOT, phosphate, lipase, amylase, fasting glucose, serum lipid panel and urinalysis/urine dipstick will be performed every four weeks (+/- 3 days) prior to each cycle. If > 2+ protein is present on urine dipstick/urinalysis, then UPC should be obtained.

3.6.1.2 Brain MRI/CT

3.6.1.2.1 A brain MRI/CT will be done monthly x 2 then every other month, within 7 days of new cycle.

OR

3.6.1.2.2 For Phase II patients enrolled to the bevacizumab failure cohort, MRI/CT will be done every 4 weeks x 4, then every 8 weeks thereafter, within 7 days of new cycle.

Note: *MRI is the preferable imaging method, CT scan may be used in cases where an MRI cannot be obtained.

3.6.1.3 All relevant information regarding drug doses, concomitant medications, and doses, measurable lesions with measurements, tumor response, laboratory examinations, and treatment-related toxicities shall be documented in the patient's medical record and flow sheets.

3.6.1.4 A complete physical exam (with vital signs) and neurologic exam (to include documentation of the patients Karnofsky Performance Status) will be performed monthly. The MDASI-BT will be completed at baseline and at the time of each evaluation that includes an imaging study.

3.6.1.5 The patient will complete the MDASI-BT (Appendix 13.4) at the time of clinical evaluation with MRI as long as the clinical therapy is being administered, unless clinical deterioration makes self-report not possible before that time. The time when patients are unable to complete the self-report questionnaires will be used as part of the study analysis. The MDASI-BT will be completed only by the patient, unless changes in vision or weakness make this difficult. If this occurs, then the caregiver or research

assistant may read the questions to the patient or assist with marking the severity number or score as described by the patient. A patient caregiver may complete the questionnaires as a patient-preference proxy if the patient's deficits preclude self-report.

- 3.6.1.6 Patients on antiviral prophylaxis treatment or positive HBV antibodies should be tested for HBV-DNA on Cycle 1 Day 1 and Day 1 of all subsequent cycles (every 28 days) to monitor for re-activation. If re-activation is confirmed, everolimus must be interrupted or discontinued according to the guidance in Table 6-3. Patients with positive HCV RNA-PCR results at screening and/or a history of past infection (even if treated and considered 'cured') should have HCV RNA-PCR testing performed on Cycle 1 Day 1 and Day 1 of all subsequent cycles (every 28 days) to monitor for reactivation. Everolimus must be discontinued if HCV reactivation is confirmed according to the guidance in Table 3-5.
- 3.6.1.7 All patients will be followed for overall survival, when possible.
- a) Patients who discontinue treatment due to progression will be followed for survival every 3 months by phone call or clinic visit.
 - b) Patients who come off therapy for reasons other than progression should be followed until progression or institution of new anti-tumor therapy. They should then be followed for survival.

3.6.2 Phase I Requirements

- 3.6.2.1 Phase I patients will be evaluated for adverse events at least weekly during their first cycle of therapy (by either phone contact or personal visit). These adverse events will be reported to the Lead PI and the BTTC Coordinating Center weekly.
- 3.6.2.2 Adverse events for subsequent cycles will be reported to BTTC Coordinating Center at the end of each cycle. In addition all serious adverse events will be reported to the BTTC Coordinating Center and the Lead PI, as directed in section 6.4

3.6.3 Phase II Requirements

- 3.6.3.1 Phase II patients will be evaluated for adverse events at the end of each cycle. In addition, all serious adverse events will be reported to the BTTC Coordinating Center and the Lead PI as directed in section 6.4

3.6.4 Follow-up

When a subject is removed from treatment as per section 3.7.1, they should continue to be followed until removed from protocol.

Follow up for survival should be done every 3 months by phone or clinic visit on patients who discontinue treatment due to progression. Those who come off treatment other than progression should be followed every 3 months by phone call or clinic visit until progression or institution of new anti-tumor therapy. Survival status will only be collected by phone or clinic visit. This data must be recorded on the appropriate follow up case report form.

3.7 CRITERIA FOR REMOVAL FROM PROTOCOL THERAPY AND OFF STUDY CRITERIA

3.7.1 Criteria for Removal from Protocol Therapy:

3.7.1.1 Progression of disease (as defined in Section 5.2.1).

Patients must be followed by the same type of brain scan, as was used for baseline tumor measurements, and will be removed from study if progression is documented after any cycle of treatment. Patients with stable disease, partial or complete response will continue on therapy as defined in Section 3.0.

3.7.1.2 Unacceptable toxicity (as defined by the investigator).

3.7.1.3 The patient may withdraw from the study at any time for any reason.

3.7.1.4 Medical or psychiatric illness which in the investigator's judgment renders the patient incapable of further therapy.

3.7.1.5 Treatment delay due to toxicity greater than 21 days measured from the start of the preceding cycle.

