3.2 PHASE II STUDY DESIGN

3.2.1 Drug Administration

All patients treated on the phase II cohorts will receive a combination of sorafenib (7 days on, 7 days off) and everolimus daily over a 28-day cycle, as follows:

Sorafenib 400 mg BID PO (days 1-7 and days 15-21)

Everolimus 5 mg PO daily (days 1-28)

There is not a defined set of maximum number of cycles that a patient may have. Patients may continue with protocol therapy until criteria for “Off Treatment” is met. See Section **3.7.1**.

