3.3 DOSE MODIFICATIONS IN PHASE I (POST CYCLE 1) AND PHASE II

Patients with stable or responding disease may be retreated at the same dose or at a reduced dose level, depending upon the adverse events observed in the current cycle and any adverse events (based on the CTCAE v.4) present on the first day of the next cycle. If multiple toxicities are seen, the dose administered in a subsequent cycle should be based on the most severe toxicity experienced in the current cycle.

Patients who experience toxicity should have laboratory testing at least weekly until the toxicity has resolved.

Toxicities will be graded according to the NCI Common Terminology Criteria for Adverse Events (CTCAE) version 4.0. If multiple toxicities are seen, the toxicity should be based on the most severe toxicity experienced. Toxicities will be defined as any of the following events occurring during treatment with sorafenib and/or everolimus and attributable to one of the study drugs:

- A. Any grade 3 thrombocytopenia, grade 4 anemia, grade 4 neutropenia, or febrile neutropenia of any grade.
- B. Any non-hematologic grade 3 or grade 4 toxicity, excluding alopecia and/or hand/foot reaction.
- C. Failure to recover from grade 3 or 4 toxicities (to grade 1 or less) to be eligible for re-treatment with sorafenib and everolimus within 14 of the last dose of sorafenib and everolimus.

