3.3.1 Within Treatment Cycles

If a patient experiences toxicities during a treatment cycle, the treatment will be immediately suspended until a grade 1 or less toxicity. If the toxicity resolves to less than or equal to grade 1 within 2 weeks, the patient will be retreated at the dose level described in Table **3-2** below. (Refer to Table **3-6** and Table **3-7** for management of everolimus-induced toxicities and Table **3-8**, Table **3-9** and Table **3-10** for management of sorafenib-induced toxicities.) If toxicity persists, the patient should be taken off study.

Two dose reductions are permitted. Doses that are reduced for sorafenib or everolimus related toxicity will not be re-escalated, even if there is minimal or no toxicity with the reduced dose. Patients whose dose has been reduced for adverse events that are subsequently not felt to be related to sorafenib or everolimus may have the dose re-escalated after completion of one cycle with toxicities less than or equal to grade 1. If any patient has further toxicities that would require additional reductions, or if treatment is held for more than 2 consecutive weeks because of ongoing

toxicity, the Study PI will assess if the patient should remain in the study (if the patient has benefited from treatment).

Table 3-2: Dose Modification Table

DOSE LEVEL	SORAFENIB	EVEROLIMUS
1 (starting dose)	400 mg BID 7 days on 7 days off	5 mg daily
-1	400 mg AM dose 200 mg PM dose 7 days on 7 days off	5 mg daily
-2	200 mg AM dose 200 mg PM dose 7 days on 7 days off	5 mg daily

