Grade 3 febrile neutropenia (not life-threatening)	Interrupt everolimus until resolution of fever and neutropenia to grade ≤ 1 . Hold further everolimus until the ANC $\geq 1,500/mm^3$ and fever has resolved. Then resume everolimus at same dose level. If febrile neutropenia recurs, discontinue everolimus.
Grade 4 febrile neutropenia (life-threatening)	Discontinue everolimus.
Any hematological or non-hematological toxicity requiring interruption for ≥ 3 weeks	Discontinue everolimus

*Grade 3 hyperlipidemia (hypercholesterolemia and/or hypertriglyceridemia) should be managed using medical therapies (see Sec. 3.3.4).

Patients whose treatment is interrupted or permanently discontinued due to an adverse event or abnormal laboratory value suspected to be related to everolimus must be followed at least weekly until the adverse event or abnormal laboratory resolves or returns to grade 1. If a patient requires a dose delay of > 21 days from the intended day of the next scheduled dose, then the patient must be discontinued from the study.

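### Section 3.7.1.5 starts its 21-day toxicity-delay clock at the previous cycle's first day, so read literally any toxicity-delayed 28-day cycle triggers removal from therapy

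*Combined protocol and SAP*

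**What the plan says.** Section 3.7.1 lists the criteria for removal from protocol therapy. Item 3.7.1.5 reads "Treatment delay due to toxicity greater than 21 days measured from the start of the preceding cycle". Unlike 3.7.1.2 and 3.7.1.4, it does not rest on investigator judgement.

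Section 3.2.1 gives sorafenib on days 1-7 and 15-21, with "everolimus daily over a 28-day cycle".

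Section 3.3.1 deals with recovery: "If the toxicity resolves to less than or equal to grade 1 within 2 weeks, the patient will be retreated", and then "If toxicity persists, the patient should be taken off study". Its next paragraph takes the case of more than two dose reductions, "or if treatment is held for more than 2 consecutive weeks because of ongoing" toxicity, and says that "the Study PI will assess if the patient should remain in the study (if the patient has benefited from treatment".

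Item C of section 3.3 has the same recovery window, counted from the most recent dosing. It describes a patient who does not "recover from grade 3 or 4 toxicities (to grade 1 or less) to be eligible for re-treatment with sorafenib and everolimus within 14"; no unit is printed after the 14.

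The text after Table 3-7 in section 3.3.7, on suspected everolimus toxicity, also uses 21 days but starts the clock elsewhere: a "dose delay of > 21 days from the intended day of the next scheduled dose" leads to discontinuation.

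**The concern.** The limit in 3.7.1.5 is shorter than the cycle it is counted over. At 21 days from the cycle's start, the patient is still inside that cycle and no later cycle can yet be late. Once the next cycle is late by a single day because of toxicity, the clock has already passed 21.

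The criterion therefore collides with 3.3.1. A site that retreats a promptly recovered patient departs from 3.7.1.5, and a site that removes the patient departs from 3.3.1. Section 6.1.8 defines any departure from the protocol as a deviation, and sections 6.3.1 and 6.4 require all deviations to be reported. The patient could also lose therapy that 3.3.1 says to resume.

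**Working it through.** The plan gives no figure to reproduce, so the check is day arithmetic.

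**Inputs.** Cycle length 28 days (3.2.1); removal limit more than 21 days from the preceding start (3.7.1.5); alternative clock, more than 21 days from the date the dose was due (3.3.7); recovery window 2 weeks (3.3.1).

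**Delayed next cycle.** Take day 1 as the cycle start, so the next cycle is due on day 29. With a delay of d days it starts on day 29 + d, which is (29 + d) - 1 = 28 + d days after the preceding start. The table assumes that the hold begins on day 29.

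| d | 28 + d | 3.7.1.5 as written (28 + d > 21) | 3.3.7 clock (d > 21) | 3.3.1 |
|---|---|---|---|---|
| 1 | 29 | removed | stays | retreat if recovered |
| 7 | 35 | removed | stays | retreat if recovered |
| 14 | 42 | removed | stays | retreat if recovered |
| 15 | 43 | removed | stays | off study, or Study PI review |
| 21 | 49 | removed | stays | off study, or Study PI review |
| 22 | 50 | removed | removed | off study, or Study PI review |

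An on-time cycle (d = 0) starts 28 days after the preceding start, but it is not a delay and is not counted.

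**Hold within a cycle.** If a hold counts as a treatment delay and dosing resumes on day r, then r - 1 days have elapsed. The criterion is met when r - 1 > 21, that is, when r > 22. A hold starting on day 8 can last 22 - 8 = 14 days without being caught. One starting on day 15 can last 22 - 15 = 7 days, and one starting on day 21 can last 1 day. Any hold starting on day 22 or later is caught.

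**One assumed patient.** Toxicity begins on day 25, is grade 1 or less on day 34, and the next cycle starts on day 35.

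- 3.3.1: 34 - 25 = 9 days to recovery, within 14, so retreat.
- 3.3 item C, taking the 14 as days: 34 - 24 = 10 days after the last everolimus dose and 34 - 21 = 13 after the last sorafenib dose, so within the window.
- 3.3.7 clock: 35 - 25 = 10 days from the first missed everolimus dose, or 35 - 29 = 6 from the due date of the cycle. The patient stays on either count.
- 3.7.1.5 as written: 35 - 1 = 34, more than 21, so removed.

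**The case against.** The best defence is that 21 days limits the length of the delay, and that the starting point only marks the window in which hold days are added up. The assumed patient then has 10 hold days and stays. That may be close to the intent, but it is not what the sentence says. The sentence measures the delay itself from the preceding cycle's start and says nothing about adding up hold days. If delay length alone is compared with 21, the starting point does no work. Section 3.3.7 shows how the rule can be written, and 3.7.1.5 does not point to it.

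Other parts of the defence stand:

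- Section 3.3.1 is about holds within cycles, and those that resume by day 22 are untouched.
- A reader might infer that every delay of 1 to 21 days puts 3.7.1.5 in conflict with 3.3.1. The documents do not support that. Once a hold exceeds 2 weeks, 3.3.1 itself calls for removal or Study PI review, so delays of 15 to 21 days are not a clear conflict.
- A reader might infer that 3.3.1 contradicts itself on toxicity beyond 2 weeks. Its two sentences read reasonably as a default and an exception, since Study PI review is tied to patients who have benefited. What is missing is a linking word.
- A reader might infer from the off-study wording in 3.3.1 and 3.3.7 that follow-up is lost. Sections 3.6.1.7 and 3.6.4 keep patients who stop therapy in follow-up, so this is a point of wording.

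**Conclusion.** The starting point in 3.7.1.5 is wrong as written. Read literally, it removes every patient whose next cycle is delayed by toxicity, and every patient whose hold within a cycle resumes after day 22. The clear conflict is with patients who recover within 2 weeks. For a hold starting on the due date these are delays of 1 to 14 days, or 29 to 42 days on a clock that stops at 21.

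This rests on the literal reading and on the 28-day cycle. For holds within a cycle, it also assumes that a hold counts as a treatment delay. Many sites would probably infer the intended rule.

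Practical exposure is small: section 2.4 marks every cohort except Group B as closed, and section 9.4 records that subjects at non-NCI sites were off treatment at Amendment C. A reader might infer an effect on efficacy results. None is claimed: stopping therapy is not in itself an event for the primary progression-free survival rates, and no sample size, power or error rate changes. Nor is any conflict with the limits in Table 3-7 claimed.

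**What to change.** Keep 21 days in 3.7.1.5 but use the starting point of section 3.3.7. Suggested text: *a toxicity delay of more than 21 days, counted from the date on which the next dose was due, unless a table in section 3.3 sets its own limit.* The exception is needed because Table 3-10 (hypertension) and Table 3-4 (hepatitis B) allow 28 days. Those limits and the ones in Tables 3-6 and 3-7 stay as they are. A separate clock from the first missed dose is best avoided, because it would be unclear for sorafenib on its off days (8-14 and 22-28).

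As an optional editorial clarification, join the two sentences in 3.3.1: *if toxicity lasts beyond 2 weeks, the patient comes off protocol therapy, unless the Study PI judges that a patient who has benefited should continue.* This keeps the present default and the benefit condition. Replacing the default with Study PI review for everyone would be a clinical policy choice that the documents do not call for.

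The cost is a few words in an amendment. No recovery window or event-specific limit changes.

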3.7.2 Off Study Criteria

3.7.2.1 Participant requests to be withdrawn from study

3.7.2.2 Institution of new anti-tumor therapy

3.7.2.3 Investigator discretion

3.7.2.4 Death

All reasons for discontinuation of treatment must be documented in the flow sheets.

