- 3-month progression free survival rate for glioblastoma patients with prior bevacizumab exposure treated with everolimus and sorafenib at the maximum tolerated dose as determined in the phase I study.
- 6-month progression free survival rate for AG patients with no prior bevacizumab exposure treated with everolimus and sorafenib at the maximum tolerated dose as determined in the phase I study.

Eligibility

- Patients with histologically proven recurrent intracranial malignant glioma will be eligible for the phase I/II component of this protocol.
- Patients must be ≥ 18 years old with a Karnofsky performance status of ≥ 60 .
- No more than 2 prior chemotherapies and 1 relapse. Prior bevacizumab therapy is allowed.

Design

- This is a phase 1 /2 study of everolimus and sorafenib in patients with recurrent high-grade gliomas.
- Phase 1: Patients will be treated with daily everolimus (days 1-28) in combination with sorafenib.
- Phase 2: Patients will be treated with the combination of sorafenib and everolimus. Sorafenib will be taken daily for 7 days on, then 7 days off. Everolimus will be taken daily.
- There is not a defined set maximum number of cycles that a patient may have. Patients may continue with protocol therapy until criteria for “Off Treatment” is met. Patients will then be followed every 3 months for survival status.
- There will be an accrual of approximately 3-6 eligible patients per cohort to the Phase I component of the study. Patients removed at any time for toxicity are evaluable. Phase I patients removed from study treatment within 28 days for reasons other than toxicity may be replaced.
- There will be a total accrual of approximately 82 eligible patients to the Phase II study (34 recurrent GBM with no prior exposure to bevacizumab, 16 recurrent Anaplastic Glioma with no prior exposure to bevacizumab, and 32 glioblastoma with prior exposure to bevacizumab).

TABLE OF CONTENTS

PRÉCIS	4
TABLE OF CONTENTS.....	6
1.0 INTRODUCTION.....	8
1.1 Objectives	8
1.2 Background.....	8
2.0 ELIGIBILITY ASSESSMENT AND ENROLLMENT	13
2.1 Eligibility Criteria	13
2.2 Screening Evaluation	17
2.3 Registration Procedures	17
2.4 Treatment Assignment and Descriptive Factors	19
2.5 Baseline Evaluation	20
3.0 STUDY IMPLEMENTATION.....	21
3.1 Phase I Study Design.....	21
3.2 Phase II Study Design.....	23
3.3 Dose Modifications in Phase I (post cycle 1) and Phase II.....	23
3.4 Questionnaires.....	34
3.5 Study Calendar.....	35
3.6 On Study Evaluation.....	37

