3.5 STUDY CALENDAR

STUDIES TO BE OBTAINED	PRE TREATMENT	DURING TREATMENT	OFF TREATMENT
Consent & HIPAA Authorization	X		
History	X ¹		
Physical exam (including vital signs) and Neurologic Examination	X ¹	X ⁵	
Karnofsky Performance Status	X ¹	X ⁵	
Blood Pressure	X ¹	X ¹⁴ , X ⁵	
CBC, with differential, platelets	X ¹	X ⁴ , X ¹⁵	
PT, PTT	X ¹		
Serum creatinine, phosphate, lipase, amylase, bilirubin, SGOT, fasting serum glucose, fasting lipid panel	X ¹	X ⁵ , X ¹⁵	
HBV-DNA, HbsAg, HBsAb, HBcAb, HCV-RNA-PCR	X ¹		
MRI or CT (brain) (X ⁵ (times 2) or X ⁵ (times 4) whichever is applicable per section 3.6.1.2)	X ¹	X ⁵ (times 2) or X ⁵ (times 4) then X ⁶ , X ¹⁶	
MDASI Symptom Assessment X ⁵ (times 2) or X ⁵ (times 4) whichever is applicable per sections 3.6.1.2 and 3.6.1.5	X ¹⁰	X ⁵ (times 2) or X ⁵ (times 4) then X ⁶	
ECG	X ³		
Chest X-ray or chest CT	X ³		

STUDIES TO BE OBTAINED	PRE TREATMENT	DURING TREATMENT	OFF TREATMENT
Urinalysis with microanalysis	X ¹		
Serum pregnancy test (β-HCG)	X ²		
UPC ratio	X ¹²	X ¹²	
Urine Dipstick/urinalysis	X ¹	X ⁵ , X ¹⁵	
HBV-DNA, HCV-RNA-PCR		X ⁹	
Prophylactic antiviral agent (i.e. Lamivudine)	X ¹¹	X ¹¹	X ¹¹
Documentation of tumor diagnosis	X		
Information on drug doses, concomitant medications and doses, (baseline and treatment related) toxicity monitoring	X	X ⁵	
Measurable lesions with measurements-tumor response (X ⁵ or X ⁶ , whichever is applicable per section 3.6.1.2)	X	X ⁵ , X ⁶	
Follow up for survival by phone or clinic visit on patients who discontinue treatment due to progression			X ⁷
Follow up for survival by phone or clinic visit, for those who come off treatment other than progression should be followed until progression or institution of new anti- tumor therapy			X ⁷
Adverse Events Notation	X	X ¹³	

X¹ To be performed within 14 days of registration

X² To be performed within 14 days prior to starting study treatment

X³ To be performed within 30 days prior to starting study treatment

X⁴ To be performed every 2 weeks during treatment

X⁵ To be performed every 4 weeks during treatment (prior to each cycle);

X⁶ To be performed every 2 months during treatment (every other month)

X⁷ To be performed every 3 months

X⁸ To be performed weekly for Phase I Cycle 1

X⁹ To be performed on Cycle 1 Day 1 and Day 1 of all subsequent cycles. Applicable to patients that are on antiviral prophylaxis treatment or positive HBV antibodies, and patients with positive

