5.1.2 Database Entry Timeframes

The following data should be entered into C3D/Labmatrix within the specified timeframes. Source documentation will be kept at the participating site.

Treatment (Cycle) Data (To include treatment, response, AE, and clinical evaluation information)	Within 40 days after the first day of each treatment cycle.
Off Treatment Data	Within 10 days after the last date of any modality of protocol treatment
Follow-up (Survival) Data	Within 52 days after the last treatment date and then every 90 days until Off Study (unless otherwise specified by the protocol)
Non-Treatment Data (May include Quality of Life questionnaires (MDASI-BT), Specimen Tracking information, Pathology Specimen Submission, etc.)	Within 10 days after each scheduled assessment, event, or activity
Off Study Data	Within 10 days after the date the patient is removed from the study.

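### New anti-tumor therapy takes a patient off study under 3.7.2.2 and ends one calendar survival row, while 3.6.1.7 continues survival follow-up past it (secondary overall survival only)

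*Combined protocol and SAP*

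**What the plan says.** Overall survival in Groups A, B and C is a secondary endpoint (1.1.2.2). It runs from registration to death from any cause (5.2.6) and is estimated by Kaplan-Meier (7.2). These provisions bear on how long survival status is collected:

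- **3.6.1.7 (General Requirements):** "All patients will be followed for overall survival, when possible". Item a): "Patients who discontinue treatment due to progression will be followed for survival every 3 months by phone call or clinic visit". Item b), for patients who come off therapy for another reason, sets follow-up "until progression or institution of new anti-tumor therapy. They should then be followed for survival".
- **Précis, Design:** after treatment ends, "Patients will then be followed every 3 months for survival status".
- **3.6.4 (Follow-up):** patients who stop for progression have survival contacts every 3 months. Those who stop for another reason are contacted on the same schedule "by phone call or clinic visit until progression or institution of new anti-tumor therapy". Nothing is said about what comes next.
- **3.5 (Study Calendar):** the second survival follow-up row reads "for those who come off treatment other than progression should be followed until progression or institution of new anti- tumor therapy".
- **3.7.2 (Off Study Criteria):** "3.7.2.2 Institution of new anti-tumor therapy", listed beside withdrawal, investigator discretion and death, with no qualification.
- **5.1.2 (Database Entry Timeframes):** survival data are due "Within 52 days after the last treatment date and then every 90 days until Off Study (unless otherwise specified by the protocol").

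**The concern.** The same event, the start of another anti-tumor therapy, is the point at which 3.6.1.7 b) moves a patient to survival follow-up and the point at which 3.7.2.2 takes the patient off study. These are conflicting rules, not a missing detail: a site can follow one only by setting aside the plain wording of the other.

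At stake is whether deaths after new therapy enter the overall survival analysis. Where a site stops collecting, the patient's survival time can only be censored at the last contact, near the start of new therapy or, under the calendar row, at progression. Patients who progress or need another treatment may well differ in prognosis from those still under observation, so the censoring could be informative. In a multicenter trial the handling could also differ from site to site, and nothing in the analysis section would show that it had.

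**Working it through.** No formula applies. The plan states no sample size, power, event count or landmark rate for overall survival, so there is no figure to reproduce. The check sets the provisions side by side for the two kinds of patient.

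| Provision | Stopped for progression | Stopped for another reason |
|---|---|---|
| 3.6.1.7 | Survival every 3 months; no end at new therapy | Followed to progression or new therapy, then for survival |
| Précis | Survival every 3 months | Survival every 3 months |
| 3.6.4 | Survival every 3 months; no end at new therapy | Contact to progression or new therapy; silent afterwards |
| Calendar | Survival every 3 months; no end at new therapy | Survival row ends at progression or new therapy |
| 3.7.2.2 | Off study at new therapy | Off study at new therapy |
| 5.1.2 | Data entry to off study unless specified otherwise | Same |

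1. *Patients who stop for another reason.* The calendar row conflicts with 3.6.1.7 b): it is a survival row, and it ends where 3.6.1.7 b) says survival follow-up begins. Section 3.6.4 conflicts only by omission. It repeats the first half of 3.6.1.7 b) and drops the second, without forbidding it.
2. *Patients who stop for progression.* Sections 3.6.1.7 a) and 3.6.4 and the calendar agree with each other. The conflict arises only through 3.7.2.2, once the patient starts another therapy.
3. *Can off study be read as off therapy?* Not comfortably. Sections 3.7.1 and 3.7.2 are separate lists, and 3.7.3 requires each status to be notified to the registration office. Section 4.1.7 bars other anticancer therapy during the study period, so 3.7.2.2 operates mainly after protocol treatment has ended, which is when survival is being collected.
4. *Does 5.1.2 settle it?* It makes off study the default end of survival data entry but gives way where the protocol specifies otherwise, and 3.6.1.7 does so. It is therefore compatible with continued follow-up. However, it does not name 3.6.1.7, and 3.7.2.2 refers to neither.
5. *Does the conflict reach the primary endpoints?* No. The Group A design (34 patients, 6-month progression-free survival) and the Group B design (32 patients, 3-month) are not built on overall survival, and Group C is a fixed cohort of 16. The provisions do not disagree on when progression follow-up ends, so no stated sample size, error rate or decision boundary changes with the reading chosen.

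**The case against.** The best answer is that the protocol already resolves this. Section 3.6.1.7 is the specific rule: it covers all patients and says in terms what happens after new therapy. The précis agrees, and 5.1.2 defers to it. The section on removal also uses its terms loosely. Under the heading of removal from therapy, 3.7.1.1 says progressing patients leave the study, yet 3.6.1.7 a) plainly goes on following them. A literal 3.7.2.2 would also cut off the 3-monthly survival contacts promised to progressing patients in three other places.

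Most of this stands. It shows that continued follow-up is the likelier intent. It does not make 3.7.2.2 or the calendar row say so: someone completing an off-study form finds nothing in 3.7.2 that points to 3.6.1.7. The qualifier in 3.6.1.7 that follow-up happens where it can reads as a practical limit, not as a rule on when a patient leaves the study.

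A reader might infer more than the documents support:

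- *That the plan censors overall survival at off study.* No provision tells the analyst to do so. The loss arises only where a site stops collecting despite 3.6.1.7.
- *That 3.6.4 forbids later survival contacts.* It only omits them.
- *That patients are now being lost.* Section 9.4 says subjects at non-NCI sites were off treatment at Amendment C. It does not say that any were alive, still in follow-up or already off study.

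**Conclusion.** The point holds as an inconsistency to be reconciled, at the level of something to consider. An unqualified off-study criterion and one calendar row contradict 3.6.1.7 and the précis on whether survival is collected after new anti-tumor therapy. Section 3.6.4 adds to the uncertainty by omission, and 5.1.2 does so through an exception that names no section.

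The effect is confined to the Kaplan-Meier estimates of secondary overall survival. Neither its size nor its direction can be determined: the documents do not say how many patients start another therapy, how many stop for reasons other than progression, or how sites have applied the rule. A reader might want a worst-case width for a landmark survival rate, but that would need an assumed count of lost patients and would bound a quantity the plan does not name. The conclusion that deaths could be lost assumes that at least one site applies 3.7.2.2 or the calendar row as written.

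**What to change.** Make four changes:

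1. Qualify 3.7.2.2 so that starting new anti-tumor therapy ends progression follow-up but not the collection of survival status.
2. Add the closing survival sentence of 3.6.1.7 b) to 3.6.4 and to the calendar row for patients who stop treatment for another reason.
3. Align 5.1.2 with this by stating that survival entries continue after new therapy, in place of the general exception.
4. In the report, give for each group the number of overall survival times censored at new therapy, so that readers can see how far any early stopping reached.

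The cost is amendment wording, with the review that any amendment needs, and continuation of the 3-monthly survival contacts that 3.6.1.7 already plans. No sample size, decision rule or treatment provision changes.
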